**1.0 Complete Research Protocol (HRP-503)****PROTOCOL TITLE:**

*Include the full protocol title.*

Response: A comparison between TiNbTaZr (GUMMETAL) and stainless-steel alloy for space closure with sliding mechanics A pilot randomized clinical trial

**VERSION NUMBER/DATE:**

*Include the version number and date of this protocol.*

Response: Version 1.5 Date: 09-25-2021

**REVISION HISTORY**

Revision #	Version Date	Summary of Changes	Consent Change?
1	1.5	Change of 0.018" Prescription Bracket only used on the maxillary canines. The remaining dentition in the maxillary arch can have either 0.018" or 0.022" Prescription Brackets.	No changes in any of the consents

**FUNDING:**

*Indicate any funding for this proposal. This should match the Funding Sources page in Click IRB.*

**Response:** Currently no funding is present

## GRANT APPLICABILITY:

*Indicate whether this protocol is funded by a grant (e.g. NIH, foundation grant). For a grant with multiple aims, indicate which aims are covered by this research proposal.*

*NOTE: This question does not apply to studies funded by a sponsor contract.*

*Include a copy of the grant proposal with your submission.*

**Response:** No Grant currently funding this study

## RESEARCH REPOSITORY:

*Indicate where the research files will be kept, including when the study has been closed. The repository should include, at minimum, copies of IRB correspondence (approval, determination letters) as well as signed consent documents. This documentation should be maintained for 3 years after the study has been closed.*

## 2.0 Study Summary

Study Title	A comparison between TiNbTaZr (GUMMETAL) and stainless-steel alloy for space closure with sliding mechanics A pilot randomized clinical trial
Study Design	Pilot randomized clinical trial
Primary Objective	1. Evaluate the total amount of canine retraction (mm) using GUMMETAL and Stainless-steel archwires 2. Evaluate the rate of canine retraction (mm/month) from T 0 -T 4 .
Secondary Objective(s)	3. Assess the 3-Dimensional control of canines during retraction from T 0 -T 4 .
Research Intervention(s)/Investigational Agent(s)	Orthodontic archwires: GUMMETAL vs. Stainless-Steel
IND/IDE #	N/A
Study Population	12-17Y11M male and female patients
Sample Size	16
Study Duration for individual participants	4 months

Study Specific Abbreviations/ Definitions	TiNbTaZr = GUMMETAL SS = Stainless Steel NiTi = Nickel Titanium
--	---

### 3.0 Objectives\*

*3.1 Describe the purpose, specific aims, or objectives of this research.*

**Response:** To investigate the maxillary canine retraction rate using GUMMETAL and Stainless steel archwires for sliding mechanics. Given GUMMETAL's relatively short presence in the orthodontic field with limited research on its various material properties and clinical applications, its potential in space closure by sliding mechanics warrants investigation.

*3.2 State the hypotheses to be tested, if applicable.*

*NOTE: A hypothesis is a specific, testable prediction about what you expect to happen in your study that corresponds with your above listed objectives.*

**Response:** We hypothesize that GUMMETAL total retraction distance and rate will be lower than the Stainless-steel group. We expect a significant difference between the groups regarding 3-Dimensional control during retraction.

### 4.0 Scientific Endpoints\*

*2.1 Describe the scientific endpoint(s), the main result or occurrence under study.*

*NOTE: Scientific endpoints are outcomes defined before the study begins to determine whether the objectives of the study have been met and to draw conclusions from the data. Include primary and secondary endpoints. Some example endpoints are: reduction of symptoms, improvement in quality of life, or survival. Your response should **not** be a date.*

**Response:** A decrease in the retraction rate (mm/month) / total retraction distance (mm) for the GUMMETAL group versus Stainless-steel group.

### 5.0 Background\*

*5.1 Provide the scientific or scholarly background, rationale, and significance of the research based on the existing literature and how it will contribute to existing knowledge. Describe any gaps in current knowledge. Include relevant preliminary findings or prior research by the investigator.*

**Response:**

Space closure mechanics

Space closure mechanics during the course of orthodontic treatment is necessary in cases with generalized spacing, congenitally missing teeth and when teeth are extracted. Space closure during treatment has shown a

correlation to longer treatment times. Orthodontist and patients prefer the shortest duration of treatment possible and this often requires reliable space closure mechanics and minimizing anchorage loss. Lack of knowledge and experience in appropriate space closure mechanics can compromise the patient's occlusion. Thus clinician should understand that space closure is determined by a combination of factors including the biomechanical forces applied, force variation, moment-magnitude, moment-force ratio, force-deflection rate and anchorage unit. Orthodontic armamentarium is vast with mechanical options to achieve adequate space closure; thus, it is important that biomechanical selection be made on an individual basis. Ribeiro et al. identify six key goals which need to be considered for space closure: 1) differential space closure-anchorage control; 2) minimum patient cooperation; 3) axial inclination control; 4) control of rotations and arch width; 5) optimum biological response; and 6) operator convenience.

Biomechanical systems traditionally used to close spaces have been friction (sliding mechanics) and frictionless (closing loop mechanics). Each method presents with its own advantages and disadvantages when it comes to space closure.

## **Orthodontic Arch wires**

### **Stainless Steel and Cobalt Chromium wires**

The ability to move teeth orthodontically via conventional fixed appliances is possible due to the orthodontic archwires. In the earliest parts of the 20th century during Edward Angle's time, gold-alloy use was ubiquitous, because gold itself was too soft for most dental applications. With the introduction of stainless-steel wires, gold-alloys became obsolete due to their prohibitive expense and inferior material qualities. Stainless steel wires were superior in their higher resistance to corrosion, excellent work-hardening properties and low coefficient of friction, making them the orthodontic standard for decades. The most commonly used type is the austenitic 18-8 stainless steel, with chromium and nickel content of 18% and 8%, respectively. Their bracket-wire frictional properties are relatively low making them a gold standard wire for sliding mechanics. The coefficient of friction can be further reduced by application of nanotechnology, such as coating the wire with nickel-phosphorus electroless film impregnated with organic fullerene-like nanoparticles of tungsten disulfide. Stainless steel's high resistance to corrosion can be attributed to the formation of a passivating oxide layer that forms on its surface and blocks oxygen diffusion to the underlying material. Contemporary commercially available stainless steel wires come in wide variety of elastic and yield strength related properties dependent on the different parameters utilized during production, such as freezing and incandescence during cold working. These wires are able to produce

higher forces during a shorter period of time due to their lesser spring back properties, thus storing less energy than nickel-titanium and beta-titanium wires. Biomechanical attachments are able to be soldered using a fastening agent to stainless steel via LASER or tungsten inert gas welding techniques.

Cobalt-chromium alloys were introduced in the 1960s originally for use as watch spring by ELGIU national company, but were quickly manufactured into orthodontic wires (Elgiloy) by the United States based company in Denver, CO; Rocky Mountain Co. These wires shared similar properties with stainless-steel in their high stiffness, however they had the advantage of being heat treatable and available in different tempers. These tempers came in four varieties (usually color-coded) depending on how much cold work had been done during manufacturing. Yellow for the soft or ductile tempers, green for semi-spring temper and red for high spring tempers. These tempers permitted high bendability which allowed for the introduction of various loops, V-bends and offsets in the archwire. Heat hardening at 482°C for seven minutes, allowed for increasing its hardness (strength) after its been shaped into the desired application. Wires which are not heat treated have a smaller spring-back than stainless steel wires. The popularity of these wires in clinical practice is due to their exceptional resistance to corrosion and tarnish, ability to be soldered/welded and inexpensive.

### Beta-Titanium wires

Further research and development with titanium alloys eventually yielded  $\beta$ -Titanium archwires with molybdenum. TMA (titanium-molybdenum alloy; Ormco CA, USA) was introduced in the 1980s for orthodontic purposes. Its material characteristics consist of high springiness, strength, good formability, welding capabilities, and ability to hold a bend, making them a brilliant choice for finishing archwires in later stages of edgewise orthodontic treatment. Krishnan et al, investigated the welding joinability properties between stainless steel wires and beta-titanium wires, concluding that the latter had better joinability due to their higher resilience and surface / structural characteristics. Beta-titanium wires have corrosion resistance similar to cobalt-chromium and stainless steel wires, along with high biocompatibility due to lack of nickel. This surface resistance can be attributed to the formation of surface passivating oxidation layer. However, this wire also has limitations and is poorly suited for applications that require flexibility and high surface roughness produces excessive friction within the bracket contact hindering sliding mechanics.

Titanium-niobium (TiNb) alloy came into the market with the designation of being a new “finishing wire” from Sybron Dental Specialties Inc., Orange, CA, USA. This material is cryogenic in nature, with superconductivity properties that have been utilized in magnets and magnetic nuclear resonance imaging applications. The alloy’s elemental

composition consists of two out of five (Ti, Nb, Ta, Zr, and Pt) non-hypersensitive elements Ti and Nb, yielding high biocompatibility. Furthermore, the material has excellent resistance to corrosion. Both of these qualities of corrosion resistance and biocompatibility attribute Ti-Nb's wide use in medicine, substituting as a reconstructive material in implant and orthopedic surgeries. Additional, this material has a low modulus of elasticity, making it ideal for distributing stresses between implants and bones. With the incorporation of niobium, the modulus of elasticity is further decreased and corrosion resistance is improved. This corrosion resistance can be attributed to Nb2O5 lining the surface layer, inhibiting the fluoride ion action responsible for immediate corrosion in the oral environment. Dalstra et al, investigated the load-deflection behavior of TiNb wires compared to stainless steel both in torsional and bending applications. Their results demonstrated that TiNb stiffness in bending is ½ of SS, and torsional properties are 1/3rd of SS. Such results indicate that TiNb could be used for creative bends without generating excessive force levels present in stainless steel wires. Additionally, they showed that TiNb spring-back was 14% lower than that of SS, whereas in torsion it was the same if not higher in some situations. Furthermore, this wire is able to be welded, thus various wire dimensions can be joined together to produce different force systems.

### Introduction of GUMMETAL

In 2003 a new  $\beta$ -Titanium alloy was developed at the Metallurgy Research Section of Toyota Central R & D Labs., Inc., Japan, named GUMMETAL. Its composition consists of a body-centered cubic crystal structure with titanium (Ti), niobium (Nb), tantalum (Ta), and zirconium (Zr). GUMMETAL's elemental composition (Ti-36%Nb-2Ta-3Zr+O) produces properties with extensive applications, especially in orthodontic therapy. These elements are contained within the IVa and Va groups on the periodic table of elements. "The remarkable characteristics of this material arise due to the juxtaposition of three electronic magic numbers: 1) a compositional average valence number of 4.24 valence electrons per atom, 2) a bond order (Bo value) of 2.87 based on the DV-x alpha cluster method, and 3) "d" electronic-orbital energy level (Md value) of 2.45 eV". This alloy merges superelasticity with superplasticity at room temperature without work hardening side effects. Additionally, its Young's modulus is extremely low (40 GPa), combined with exceptionally high tensile strength (1100 MPa) producing a material with characteristics previously thought impossible. In comparison, SS has a young modulus of 200 GPa, CoCr at 170 GPa, NiTi at 105 GPa, and Beta-Titanium alloys at 85 GPa. When looking at tensile strength in MPa, stainless steel is at 860 MPa, CoCr at 1000 MPa, NiTi at 700 MPa and Beta-titanium alloy at 860 MPa.

The main feature of this material is the ease to do plastic deformation without disrupting the crystalline structure along with lack of stress-

induced transformations such as NiTi alloys, meaning it possesses true elastic deformation without hysteresis. Such material characteristics result in a metal that does not follow Hooke's law, with behaviors curving to and from the yield point. Unlike SS, Co-Cr, and NiTi which all possess either Chromium or Nickel and have been known to have biocompatibility and toxicity issues, GUMMETAL's elemental constituents are biocompatible. The frictional properties between wire and bracket interface is approximately half that of other titanium wires with appropriate surface treatment according to Toyota R&D department and Takada et al.

Orthodontic archwire manufactured out of GUMMETAL appeared on the market in 2010 by Rocky Mountain Morita Corporation. The manufacturing process avoids high temperatures and alternatively utilizes cold-working for diluting and wire-drawing, which produces a marble-like microstructure that allows the wire to be plastically deformed without dislocating the crystals. Orthodontic application for this new wire is appears promising when considering the properties of the inherent material and its possibilities in tooth movement. These wires are extremely flexible, and super-elastic, they are able to bend with ease and hold that bend, there is an equal loading and unloading force without hysteresis (allowing for controlled orthodontic force), not susceptible to work hardening (intraoral breakage is rare), free of any toxic elements (nickel and heavy metals), generates half the friction of other titanium alloys and possess exceptional tensile strength. Until GUMMETAL, there was no ideal orthodontic wire with all of these characteristics, various wire sizes and types were used for different purposes during treatment (NiTi for leveling and aligning and SS/TMA for finishing and detailing).

Given the low Young's modulus, high deformation intraorally to a round or even a rectangular wire would produce a small force. Such small forces would be appropriate in early stages of treating crowded teeth. Shorter duration of treatment could be possible if rectangular GUMMETAL wires are able to be used earlier in treatment due to the high elasticity, since torque control could be initiated much earlier. Thus, the ability to control teeth in 3-Dimensions is very possible with GUMMETAL, since it can be used in all stages of active treatment, reducing treatment duration and office visits.

Current research has investigated GUMMETAL wires compared to NiTi wires in their effectiveness as an initial archwire in aligning teeth, concluding that GUMMETAL is an adequate alternative to NiTi for the initial orthodontic treatment. No research studies have been published regarding space closure utilizing GUMMETAL for canine retraction. Likewise, there is no published studies on the use of preformed GUMMETAL loop archwires or sliding mechanics for space closure. When considering loop space closure mechanics, it is important that the

archwire have high tensile strength, be able to deflect and produce light continuous forces during the retraction phase of treatment. Given GUMMETAL's high tensile strength (1000-1100MPa), ease of formability and low load/deflection ratio, makes them an ideal candidate for complex loop configurations.

### **Properties of GUMMETAL and statement of the problem**

GUMMETAL's non-linear superelastic properties allow for equal loading and unloading force delivery without any energy loss. Its ductility is 10 times greater than conventional metals making it super-plastic and ideal for forming and bending. Additionally, it doesn't experience work hardening during processing making it strong and durable, with little risk of intraoral breakage. Regarding friction based sliding mechanics, GUMMETAL's friction properties have only been scarcely investigated. Some researchers have claimed that its friction coefficient is low and it is therefore adequate for sliding mechanics. However, they compared GUMMETAL to other titanium wires, stating that the frictional coefficient is half for GUMMETAL depending on the surface treatment. The potential for this wire to become a transitional archwire for final leveling and aligning and then utilized for space closure is high. Thus, it could have benefit to clinicians in areas of cost effectiveness with reduced need for multiple types of wires and potentially efficiency of treatment. Both, In-vitro and clinical studies are needed to understand the effects of GUMMETAL wires for space closure using both friction sliding mechanics and frictionless closing loops mechanics.

### **2) PURPOSE OF THE RESEARCH**

Orthodontic biomaterials are continuously going through research and development, in hopes of producing an archwire that marries the properties of NiTi and SS.

GUMMETAL's introduction to the orthodontic field is relatively short. Limited research has been published regarding this wire and its application. Literature has shown that it is comparable to NiTi in the initial early stages of leveling and aligning and relieving crowding, in addition to having advantages over NiTi with its formability and lack of immunogenicity. No current publications have investigated the effects of GUMMETAL wires on maxillary canine retraction with sliding mechanics.

The purpose of this study is to investigate the effects of GUMMETAL wire on space closure using sliding mechanics. Furthermore, no studies have compared GUMMETAL sliding mechanics to that of Stainless Steel, which has remained a gold standard. Evaluation of 3D tooth control by GUMMETAL remains to be investigated.

## 6.0 Study Design\*

6.1 *Describe and explain the study design (e.g. case-control, cross-sectional, ethnographic, experimental, interventional, longitudinal, observational).*

Response: This will be a randomized pilot split-mouth clinical trial of patients with spaces  $\geq$  3mm distal to the maxillary canines in need of closure through sliding mechanics. The sample consists of adolescent patients regardless of Angle's molar malocclusion who are receiving comprehensive full fixed appliance orthodontic treatment. Preformed conjoint archwires half being GUMMETAL and the other half SS, will be utilized. Each patient will have one side of the maxilla randomly allocated into the SS or GUMMETAL treatment group. The study will follow a split-mouth design to reduce the confounding variables from patient to patient on space closure mechanics. The maxillary arch in each subject will be randomized into a SS side or GM side using a random number

generator. Spaces will be measured at; T0 is initial records, T1 is initiation of space closure, T2 will be 4 weeks after the initiation of space closure, T3 is another 4 weeks of space closure evaluation and T4 will be the final evaluation of space closure after 4 weeks from T3, via 3D intraoral scans of maxillary arches. Space measurement and calculations will utilize 3Shape software to measure the distance of canine movement based off the distal surface. Sliding mechanics will be activated through NiTi coil springs from the maxillary canines to the maxillary molars. The force will be standardized to 150 gms and will be measured each visit. The same provider will activate the NiTi coil spring for retraction, along with data collection. Superimposition of scans will be utilized to assess outcome measures.

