## **13.0 Procedures Involved\***

**13.1 Provide a description of **all research procedures or activities** being performed and when they are performed once a subject is screened and determined to be eligible. Provide as much detail as possible.**

*NOTE: This should serve as a blueprint for your study and include enough detail so that another investigator could pick up your protocol and replicate the research. For studies that have multiple or complex visits or procedures, consider the addition of a schedule of events table in in your response.*

**Response:** Once the subject has been screened and been deemed eligible to participate in the study the following procedures will take place.

Standard of Care:

- Conventional Full Fixed appliances will be bonded to all permanent teeth (either 0.018" or 0.022" MBT prescription brackets), the maxillary canine bracket prescription will be 0.018" MBT (0.018" straight wire brackets MBT; 3M Oral Care, St. Paul, MN, USA)
- Phase of leveling and aligning will proceed through standard archwire progression, until 0.016 x 0.022" sized wire is able to be engaged.

- Sliding mechanics of canine retraction utilizing NiTi Closed Coil Springs to produce 150g of retraction force, utilizing the first molars and premolars as anchoring units.
- Correx Orthodontic Gauge will be utilized to verify 150g of force generation.

Research:

- A split mouth design will be utilized per patient, randomly assigning the upper left and right sides of the maxilla, through a random number generator.
- Split archwire design will utilize a crimpable binding mechanism to allow for joining of the SS and GUMMETAL wires together dividing at the junction of the maxillary central incisors.
- Patient's occlusion will be disclused to prevent interferences prior to retraction mechanics utilizing bite-turbos on the buccal inclines of the palatal cusps of the maxillary first molars.
- Intraoral scan will be taken utilizing an iTero intraoral scanner prior to beginning retracting mechanics on the upper canines (this will be timepoint T0).
  - Appointment date, patient name, age, sex and position of Canine T0 will be collected into the data sheet.
- If there is a need for absolute anchorage, miniscrews will be utilized on a per case basis.
- T1 will begin canine retraction on both side of the maxillary arch.
  - Intraoral scan will be done

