## 20.0 Data Management and Analysis\*

*20.1 Describe the data analysis plan, including any statistical procedures. This section applies to both quantitative and qualitative analysis.*

**Response:** Statistical analysis will be performed using the Statistical Package for the Social Sciences (SPSS). To assess normality of all quantitative variable distributions the Shapiro-Wilk Test will be utilized. To evaluate statistical significance in the difference between experimental and control groups for preoperative and postoperative measurements, a paired t-test will be used. The level of significance will be set to  $p \leq 0.05$  and to assess inter- and intraobserver reliability the intraclass correlation coefficients were obtained.

*20.2 If applicable, provide a power analysis.*

*NOTE: This may not apply to certain types of studies, including chart/records reviews, survey studies, or observational studies. This question is asked to elicit whether the investigator has an adequate sample size to achieve the study objectives and justify a conclusion.*

**Response:** Sample size estimation: Based on a power of 80% and a significance level of 0.05, it was determined that a sample of size of 16 would be sufficient to detect a difference of 0.5mm or greater.

*20.3 Describe any procedures that will be used for quality control of collected data.*

**Response:** The research examiner and supervisors will be ensuring that the data is good quality and is adequate for analysis. All patient records and data will be encrypted, deidentified and properly stored and secured on our computer network.

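### No left/right balancing of the wire side is described for the 16 patients, and the paired t-test has no side term; a concealed 8:8 list plus a side term is a cheap improvement

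*Combined protocol and SAP*

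**What the plan says.** Section 6.1 describes a split-mouth trial: "Each patient will have one side of the maxilla randomly allocated into the SS or GUMMETAL treatment group". The method is given as "The maxillary arch in each subject will be randomized into a SS side or GM side using a random number" generator. Section 13.1 says the same: "randomly assigning the upper left and right sides of the maxilla, through a random number generator". Neither section mentions a block, a prepared list, a target number of patients with GUMMETAL on each side, or concealment.

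On conduct, 6.1 states "The same provider will activate the NiTi coil spring for retraction, along with data collection". Force is standardised to 150 g and measured at each visit (6.1), with a gauge (13.1). Bite-turbos separate the occlusion before retraction starts (13.1).

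On analysis, 20.1 says that "a paired t-test will be used" and names no side term. Section 20.2 gives the size: "Based on a power of 80% and a significance level of 0.05", "a sample of size of 16 would be sufficient to detect a difference of 0.5mm or greater". It states no SD. Section 22.3 discards the data of patients who withdraw.

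**The concern.** Pairing removes differences between patients. It does not remove a left-right difference that patients share, such as one arising from operator access or from how the springs are activated. Within each patient wire and side coincide, so only the allocation across patients separates them. Two consequences follow if such a difference exists:

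- **Uneven split.** Part of the side difference is carried into the wire estimate of this trial.
- **Any split, including 8:8.** The side difference adds variation to the paired differences, and the paired t-test counts it as error.

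At stake are the interpretation of a small trial that happens to draw a poor split, and some power.

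**Working it through.** **Inputs.** n = 16 pairs, target 0.5 mm, power 80%, significance level 0.05 (20.2). Two-sided testing is assumed: 20.1 does not state it, and the hypothesis in 3.2 is directional. The left-right difference δ is not in the documents; 0.1 to 0.5 mm is an assumed range.

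**Plan's own figure.** The 16 cannot be reproduced, because no SD is given. Solving the paired t-test (noncentral t, df 15) for 80% power gives an SD of the paired difference of 0.667 mm. One-sided testing would give 0.767 mm.

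**Split under independent draws.** The number k with GUMMETAL on the left is Binomial(16, 0.5).

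| Split | P(this or worse) | Shift in wire estimate |
|---|---|---|
| 8:8 | 19.6% (exactly) | 0 |
| 10:6 | 45.4% | 0.250 δ |
| 11:5 | 21.0% | 0.375 δ |
| 12:4 | 7.7% | 0.500 δ |

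**Shift given the split.** Model: paired difference (GUMMETAL minus steel) = wire effect ± δ + error, with + when GUMMETAL is on the left. The unadjusted mean is shifted by δ(2k − 16)/16. At 12:4 this is 8/16 = 0.5 δ. For δ = 0.3 mm the shift is 0.15 mm, or 0.15/0.5 = 30% of the target. In simulation at 12:4, the planned test's type I error is 7.7% for δ = 0.2 mm and about 10.7% for δ = 0.3 mm. When the imbalance works against the wire effect, power is about 58% and 44%.

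**Over all draws.** Simulated type I error of the planned test is about 5.0% for every δ tried, and the shift averages zero.

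**Power averaged over splits.** If 0.667 mm contains no side difference, the SD seen by the planned test is √(0.667² + δ²), with df 15.

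| δ (mm) | SD (mm) | Planned test | 8:8 with side term (SD 0.667, df 14) |
|---|---|---|---|
| 0 | 0.667 | 80.0% | 79.6% |
| 0.1 | 0.675 | 79.1% | 79.6% |
| 0.2 | 0.696 | 76.5% | 79.6% |
| 0.3 | 0.731 | 72.4% | 79.6% |
| 0.5 | 0.834 | 61.2% | 79.6% |

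**The other reading of the SD.** If 0.667 mm already contains δ = 0.3 mm, the planned test keeps 80%. The residual SD with a side term is √(0.667² − 0.3²) = 0.596 mm, and 8:8 with a side term (df 14) gives 87.7%.

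**Which part of the remedy does what.**
- An 8:8 list without a side term gives about 74% power at δ = 0.3 mm and is conservative (type I error about 3.3%).
- A side term without the list removes the shift. Its relative efficiency is 1 − ((2k − 16)/16)², so power is 67.6% at 12:4 and 76.7% on average.
- Both together give 79.6%.

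**The case against.** The strongest reply is that randomisation already deals with this. A reader might infer that the planned test is biased or exceeds its 5% level. The documents do not support that: over the randomisation it is unbiased and holds its level. What remains is the shift conditional on the split that the trial actually draws, which its readers will see.

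A reader might also infer that the protocol prescribes independent draws. It does not say so; a random number generator can also produce a balanced list. The probabilities above therefore depend on that assumption. The text supports only that no balancing is described.

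A third tempting reading is that power falls to 72%. That figure needs a 0.3 mm side difference, which the documents do not give, and an SD free of side effects, which they do not state. It is also an average over splits, not the power at 12:4. The gauge check and the bite-turbos may keep any side difference small, and at 0.1 mm the planned test loses less than one point.

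Finally, most of the power gain comes from the side term, and a fixed list brings its own problem: late assignments become predictable. Under 8.3 and 13.1 the research examiner both judges eligibility and activates the springs, so this objection stands unless the list is concealed.

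**Conclusion.** The point holds as a cheap improvement, not as a flaw that invalidates the planned analysis. The plan describes no left/right balancing and no side term. Under independent draws, about one trial in five would end at 11:5 or worse, and a shared side difference would then shift the estimate by at least 37.5% of its size. The possible gain in average power runs from about half a point (δ = 0.1 mm) to about 18 points (δ = 0.5 mm, as large as the target effect itself). With no side difference there is a loss of 0.4 points. These figures rest on a back-solved SD of 0.667 mm, two-sided testing and an assumed δ.

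**What to change.** - **Sections 6.1 and 13.1.** Specify a list made before the first patient, with 8 GUMMETAL-left and 8 GUMMETAL-right in random order. It should be held by someone who neither enrols patients nor judges eligibility. Each assignment is opened only after enrolment, when the split wire is placed. If a balanced list is already intended, say so.
- **Section 20.1.** Estimate the wire effect with a side term, as the simple average of the mean paired differences in the GUMMETAL-left and GUMMETAL-right groups.

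The side term is also needed because 22.3 discards withdrawn patients, so completers can drift from 8:8. With two random losses the chance of an 8:6 split is 2 × 28/120 = 46.7%. The side term still removes the shift.

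**Cost.** A prepared list, a person to hold it, and one degree of freedom (80.0% to 79.6% power if there is no side difference). No visit or procedure changes.
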